Protocol Summary

This document represents the protocol summary for the study on human subjects. The study will be carried out in accordance with ICH GCP, National Standard of the Russian Federation GOST 52379-2005 "Good Clinical Practice", Helsinki Declaration of World Medical Association, relevant requirements of the regulatory authorities as well as the study procedures.

Title of Study

Multicenter double-blind placebo-controlled parallel-group randomized clinical study of efficacy and safety of Tenoten for children liquid dosage form therapy in infants with sequelae of perinatal brain injury.

Phase: III

Sponsor: OOO "NPF "Materia Medica Holding", Moscow, Russia

Protocol No. MMH-TD-004

Study purposes

- To assess the clinical efficacy of Tenoten for children liquid dosage form therapy (10 oral drops per day for 12 weeks) in infants with sequelae of perinatal brain injury (mild-to-moderate cerebral hypoxia-ischemia and/or mild-to-moderate intracranial hemorrhage).
- To assess the safety of Tenoten for children liquid dosage form therapy (10 oral drops per day for 12 weeks) in infants with sequelae of perinatal brain injury (mild-to-moderate cerebral hypoxia-ischemia and/or mild-to-moderate intracranial hemorrhage).

Endpoints

Primary endpoint

1. Percentage of patients with a 4 and more point increase of the total score according to Jurba-Mastyukova psychomotor development scale by the end of the treatment course compared to baseline.

Secondary endpoints

1. Percentage of patients with normal psychomotor development (≥ 27 scores on Jurba-Mastyukova scale) by the end of the treatment course compared to baseline.
2. Mean Cognitive adaptive test/Clinical linguistic and auditory milestone scale (CAT/CLAMS) by the end of the treatment course compared to baseline.

3. Percentage of patients with normal psychomotor development (CATS/CLAMS + Gross motor developmental quotients score ≥ 75) by the end of the treatment course compared to baseline.
4. Clinical Global Impression scale - Efficacy Index (CGI-EI) score by the end of the treatment course.

Safety assessment

- Adverse events during the treatment, their severity, treatment relatedness, and outcomes.

Study design

Study design: multicenter, double-blind, placebo-controlled, parallel-group, randomized clinical study to assess efficacy and safety of the study therapy.

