The study will enroll children of both genders aged from 29 days (end of neonatal period) up to 9 months on outpatient neurologist's observation due to sequelae of perinatal brain injury (mild-to-moderate cerebral hypoxia-ischemia and/or mild-to-moderate intracranial hemorrhage). The subjects of the study are not to be scheduled for any other treatments besides the investigated therapy within 12 weeks of the trial.

After parent/adoptive parent has signed the patient information sheet (informed consent form) the subject's medical history will be collected, physical examination will be performed, body weight, length, and head circumference will be measured. The infant neurological status will be assessed including psychomotor development according to Jurba-Mastyukova scale and Clinical Adaptive Test/Clinical Linguistic and Auditory Milestone (CAT/CLAMS) scale. Concomitant therapy will be recorded. If the subject meets inclusion criteria and has no exclusion criteria he/she will be included in the study and randomized at Visit 1 into one of the two groups: group 1 will receive Tenoten for children (oral drops) 10 oral drops per day for 12 weeks; group 2 - Placebo 10 oral drops per day for 12 weeks.

The subject will be observed for 12 weeks during which he/she will be examined by neurologist every 4 weeks (Visits 2, 3 and 4) in order to evaluate changes in physical and neuropsychological development, changes in neurological status, and to record potential adverse events, study treatment compliance.

At the final visit (Visit 4, Week 12) the neurologist will evaluate motor and mental development, fill in Jurba-Mastyukova and CAT/CLAMS scales, record adverse events, and assess the therapy compliance. Then the Clinical Global Impression – Efficacy Index (CGI-EI) scale will be filled in.

Music therapy, herbal baths, gymnastics and tactile stimulation based on the child's age are allowed during the study.

If the prohibited medicines are required for patients they will be withdrawn from the study and it will be considered as the absence of efficacy.

Inclusion and exclusion criteria

Inclusion criteria

1. Full-term infants aged 29 days to 9 months¹.
2. Diagnosis of sequelae of perinatal brain injury (mild-to-moderate cerebral hypoxia-ischemia and/or mild-to-moderate intracranial hemorrhage).
3. Jurba-Mastyukova total score < 27 and > 12.
4. Physical development parameters within 25-27 centiles.
5. Neurologist's outpatient observation.

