2. Acute infectious disease, exacerbation / decompensation of diseases that may prevent the patients' participation in the clinical study.
3. Allergy/intolerance of any of the study treatment medications components.
4. Drug addiction, alcohol use in the volume over 2 alcohol units/day by the subject's parent(s)/adoptive parent(s).
5. Mental disorders of the patient's parent(s)/adoptive parent(s).
6. Participation in other clinical studies for a period prior to and during the course of this trial.
7. Other conditions complicating the subject's participation in the study (cannot make regular medical visits, moving, etc.).
8. Subjects whose parent(s)/adoptive parent(s), from the investigator's point of view, will not follow the study requirements or comply with the dosing regimen.
9. Patients whose parent(s)/adoptive parent(s) are related research staff of the clinical investigative site who are directly involved in the study or is a close relative of the investigator. Close relatives include spouse, parents, children or brothers (sisters) regardless of whether they are biological or adoptive ones.
10. Patients whose parent(s)/adoptive parent(s) is working in OOO "NPF "Materia Medica Holding", i.e. is the company official, temporary contract worker or an appointed official responsible for the study or their close relatives.

Discontinuation criteria

1. Inability or refusal of parent(s)/adoptive parent(s) to compliance the protocol.
2. Necessity in the products not allowed within the study.
3. Development of an adverse event requiring the product discontinuation.
4. Parents'/adoptive parents' wish to terminate the study early due to lack of therapeutic efficacy or for any other reason.
5. Cases not specified by the protocol when, according to the investigator, further subject's participation is dangerous.
6. Enrollment of an ineligible subject.

Number of subjects

Signing informed consent by the parent(s)/adoptive parent(s) of 184 patients is planned; this is supposed to assure completion of all protocol procedures by at least 144 subjects.

Treatment

Group 1

Name: Tenoten for children

Active ingredient (per 1.0 mL): affinity purified antibodies to brain-specific S-100 protein - 0.006 g*

* administered as a mixture of three active water dilutions of the substance diluted respectively 100¹², 100³⁰, 100⁵⁰ times

Excipients: Maltitol – 0.06 g; glycerol – 0.03 g; potassium sorbate – 0.00165 g; citric acid anhydrous – 0.0002 g; purified water – up to 1.0 mL

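### Does the plan need changing because only infants who need prohibited medicines have a stated outcome, while other early exits and missing Week 12 scores have none?

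*Combined protocol and SAP*

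**What the plan says.** The Protocol Summary opens by stating its own scope: "This document represents the protocol summary for the study on human subjects". The primary endpoint is binary: "Percentage of patients with a 4 and more point increase of the total score according to Jurba-Mastyukova psychomotor development scale", from baseline to the end of treatment.

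Under Study design, "The subject will be observed for 12 weeks during which he/she will be examined by neurologist every 4 weeks". The Schedule of study procedures has the Jurba-Mastyukova and CAT/CLAMS scales scored at all four visits. At the last visit only, the "Efficacy Index (CGI-EI) scale will be filled in".

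The same section gives the one outcome rule for an infant who leaves early. If prohibited medicines are required, "they will be withdrawn from the study and it will be considered as the absence of efficacy".

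Discontinuation criteria lists six reasons. Item 2 is the need for prohibited products, which the rule above covers. Item 3 is "Development of an adverse event requiring the product discontinuation". Item 4 is the parents' "wish to terminate the study early due to lack of therapeutic efficacy or for any other reason". Item 5 covers cases where, "according to the investigator, further subject's participation is dangerous". Items 1 and 6 are non-compliance and ineligible enrolment. None of these five has an outcome attached.

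Statistical Analyses plans efficacy on two sets, the FAS (labelled ITT) and the PP set. It defines neither and does not mention missing scores. The sample size of 72 per group is on the PP basis. A 22% allowance for losses at screening and on study raises recruitment to 92 per group.

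**The concern.** The plan seems to treat like cases differently. An infant who needs a prohibited medicine counts as an efficacy failure, while one whose parents stop because the product is not working has no stated result. Because the primary endpoint is scored at Week 12, every infant without a Week 12 score must be counted as a failure, imputed or left out, and the text does not choose between these.

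The choice can matter. If failures leave and are dropped from the comparison, the arm that loses more of them looks better than it is. If the product works and more placebo failures leave, the same handling understates the benefit. A rule fixed only after the data are seen would also leave room for choice. The plan itself expects losses, with 184 consents intended to give 144 completers.

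**Working it through.** **The plan's own figure.** The inputs are 72 per group and a 22% loss (Statistical Analyses). 72/(1 − 0.22) = 92.3 per group and 144/0.78 = 184.6 in total, against the stated 92 and 184. Conversely, 1 − 144/184 = 21.7%. The figure reproduces. The 22% includes screening losses, so 20 losses per arm after randomisation is an upper bound.

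**What the handling could do to the estimate.** Suppose 92 are randomised per arm and 20 are lost in each, with the planned 22 points holding among completers.
- Completers only: 22.0 points.
- All losses counted as failures: 22 × 72/92 = 17.2 points.
- With assumed completer rates of 62% and 40%, and losses of 10 active and 30 placebo counted as failures: 0.62 × 82/92 − 0.40 × 62/92 = 0.283.
- With those losses reversed: 0.62 × 62/92 − 0.40 × 82/92 = 0.061.

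So an unstated rule can move the result when losses are heavy and lopsided. The lopsided splits are invented to show sensitivity; nothing in the documents predicts them.

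**Bias under a completers-only analysis.** Assume 40% true response in both arms, so 60% fail, and that every lost infant is a failure. The apparent rate in an arm is 0.40/(1 − share lost). The last column is the rejection rate of a two-sided 5% pooled z test, from 1,000,000 simulated trials with 92 randomised per arm.

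| Losses, arm A vs arm B | Spurious difference | Rejection rate |
|---|---|---|
| 10% vs 5% of failures | 0.40/0.94 − 0.40/0.97 = 0.013 | 5.4% |
| 15% vs 5% of failures | 0.40/0.91 − 0.40/0.97 = 0.027 | 6.6% |
| 10% vs 5% of all randomised | 0.40/0.90 − 0.40/0.95 = 0.023 | 6.2% |
| 15% vs 5% of all randomised | 0.40/0.85 − 0.40/0.95 = 0.050 | 9.9% |

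In the opposite direction, take true rates of 62% and 40%, with 5% of product failures and 10% of placebo failures lost. The apparent difference is 0.62/(1 − 0.38 × 0.05) − 0.40/(1 − 0.60 × 0.10) = 0.206. With 15% of placebo failures lost it is 0.192. The true 22 points shrinks to 20.6 or 19.2.

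**Whether that analysis is the planned one.** It is not stated anywhere. The plan commits to an ITT analysis on the FAS beside the PP analysis, and completers-only is closer to the latter. If lost infants really are failures, as the table assumes, counting them as failures gives 0.40 against 0.40 and the spurious difference vanishes. The table also gives no credit for the existing prohibited-medicine rule, which on its natural reading already keeps one group of failures in the count.

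**Whether follow-up after exit is a real gap.** The prohibited-medicine rule and item 4 describe leaving the study, and item 5 concerns continued participation. Only item 3 speaks of stopping the product, and there no text says that visits end. For prohibited-medicine exits, continued visits would not change a result already treated as absence of efficacy. For item 4, they may be impossible if the parents have withdrawn consent.

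**The case for a change.** The best case for acting is that two analysts could follow this text and report different primary results. The prohibited-medicine rule is not expressly tied to the 4-point endpoint or to either analysis set. An ITT label alone does not say how a missing score is counted. Lack of efficacy is named as an exit reason yet left without a result. Power is stated only for PP completers. Assuming placebo rates of 0.23 to 0.53, power is 76–80% with 72 completers per arm. It falls to 65–76% if 20 of 92 per arm are lost and all are counted as failures.

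The omission stands, and so does the arithmetic. What does not follow is that a stated rule is wrong. Defining the sets, assigning outcomes by exit reason and saying how CGI-EI is handled would only write down detail that a summary can leave to a fuller protocol or SAP. A repeated-measures model, a tipping-point analysis and a particular handling of adverse-event exits are matters of estimand or preference. The power figures show a cost of counting losses as failures, but the plan claims 80% only on the PP basis. Part of the shortfall also has nothing to do with losses: with none at all, 80% power already takes 72 to 80 per arm over those placebo rates.

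The two sets of figures also rest on different premises. The bias table takes lost infants to be failures, whereas the dilution argument takes the 22 points to hold among completers and treats scoring losses as failures as a cost. The two should not be added together.

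**Conclusion.** No change to the plan. The text is silent on the outcome of five of the six exit reasons and on missing Week 12 scores, but this is a gap that analysts can fill sensibly. The ITT commitment points to keeping randomised infants in the FAS. The prohibited-medicine rule extends naturally to exits for lack of efficacy as non-response, although that reading is an inference. The remaining cases are ordinary SAP detail to be settled before unblinding, and a fuller document may already settle them.

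The size of any bias is unknown. Under the assumed 40% response, with all losses failures and a completers-only analysis that the plan does not state, the false-positive rate is 5.4–6.6% in the modest cases and 9.9% in the extreme one. The conclusion rests on this document being the summary it says it is. If no fuller text existed and the primary analysis did drop early leavers, the point would carry more weight.

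### Inclusion criterion 4 prints a two-point centile band (25-27) that cannot be squared with at least 144 completers from 184 consents and is very unlikely to be the intended range

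*Combined protocol and SAP*

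**What the plan says.** Item 4 of the inclusion criteria reads "Physical development parameters within 25-27 centiles". No other section restates, explains or changes this range.

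The Study design section sets the order of events. After the parent has signed consent, "body weight, length, and head circumference will be measured"; the Schedule of study procedures has physical development rated by centile tables at Visit 1 and again at Visit 4. Eligibility is then decided: "If the subject meets inclusion criteria and has no exclusion criteria he/she will be included in the study and randomized at Visit 1". An infant who fails criterion 4 has therefore already been counted as a consent.

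On numbers, the Number of subjects section states "Signing informed consent by the parent(s)/adoptive parent(s) of 184 patients is planned", which is meant to secure "completion of all protocol procedures by at least 144 subjects". The Statistical Analyses section gives 72 per group for the PP analysis and a single loss figure of at least 22%, covering screening and the study period together.

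Two other items bear on the point. Inclusion criterion 5 is "Neurologist's outpatient observation". Discontinuation criterion 6 is "Enrollment of an ineligible subject".

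**The concern.** A band from the 25th to the 27th centile is only two centile points wide. By the definition of a centile it holds very few children, yet the plan allows only about one consented infant in five to be lost for all reasons combined. Both cannot be right.

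The line is a binding threshold, so the error has a cost whichever way a site handles it. A site that follows the text will reject nearly every infant it screens. A site that applies a wider range will enrol infants who formally fail an inclusion criterion, and discontinuation criterion 6 covers such infants. The intended range cannot be recovered from the document, so a site would have to guess it.

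**Working it through.** **Inputs.** Band 25-27 (inclusion criterion 4); 184 consents and at least 144 completers (Number of subjects); 72 per group and 22% loss at screening and during the study (Statistical Analyses). The centile distribution of the consented infants is not given and has to be assumed.

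**1. The plan's own figure.** 2 × 72 = 144. Retention needed: 144/184 = 0.783, so the loss allowed is 40/184 = 21.7%, in line with the stated 22%. In the other direction, 184 × 0.78 = 143.5, about 144. The recruitment figure reproduces. Because screening failures sit inside the 22%, at least 78.3% of consented infants must pass criterion 4, before any other loss is counted.

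**2. What the printed band admits, reference-like infants, one measurement.**
- Bounds taken as points: 0.27 − 0.25 = 0.02, and 184 × 0.02 = 3.7 infants.
- Both end centiles counted as whole bands: 0.03, and 184 × 0.03 = 5.5 infants.
- Consents needed for 144 infants to pass, with no later loss: 144/0.02 = 7,200, or 144/0.03 = 4,800.
- Concentration needed relative to the reference share: 0.783/0.02 = 39 times, or 0.783/0.03 = 26 times.

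One measurement is the lenient reading. Requiring weight, length and head circumference all to comply could only lower the count.

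**3. Does the result depend on the reference assumption?** Let the infants' z-scores be normal with mean m and SD s. Then

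p = Φ((z27 − m)/s) − Φ((z25 − m)/s), with z25 = −0.6745 and z27 = −0.6128.

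| Assumed infants | p | Of 184 |
|---|---|---|
| Reference: m = 0, s = 1 | 0.0200 | 3.7 |
| Centred on the band: m = −0.643, s = 1 | 0.0246 | 4.5 |
| Centred, half the spread: m = −0.643, s = 0.5 | 0.0492 | 9.0 |

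To reach p = 0.783 with perfect centring, the half-width of the band in z units, (0.6745 − 0.6128)/2 = 0.0308, must equal about 1.23 s. That gives s = 0.025, one fortieth of the reference spread. No plausible group of infants is that uniform without selection on growth before consent, and the document describes no such selection.

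**The case against.** **The digits may not be the sponsor's.** The range appears once, in text extracted from a PDF, and the file describes itself as a summary: "This document represents the protocol summary for the study on human subjects". The full protocol may carry another range. This stands as a condition on the conclusion. Nothing points to a misreading of these particular digits, but they should be checked first.

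**Infants may be chosen before consent.** They are already under a neurologist's care, so some informal selection is possible. But being under a neurologist's observation is not selection on growth, and the measurements are placed after consent.

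**The parameters are inferable, and a summary need not spell out everything.** This largely stands. Weight, length and head circumference are the measurements listed, and silence on whether one or all must comply is missing detail in a summary, not a demonstrated gap in the protocol.

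**Stronger readings that a reader might infer and that the document does not support:**
- *That the upper bound alone must be wrong, since no band ending at 27 could work.* In a reference-like group such a band passes at most 184 × 0.27 = 49.7 infants. That cap depends on the assumption: a downward shift of about 1.4 SD would put some 78% below the 27th centile. The shift would not rescue 25-27, but it means that neither bound can be taken as the correct one.
- *That a particular wider range was meant, and that the 22% loss or the 184 consents are therefore wrong.* No other range appears in the document, so no revised consent number can be derived from it.
- *That the trial's comparison is compromised.* The criterion acts before allocation and equally in both arms. It does not enter the endpoint, the assumed difference, alpha or power. The document does not show which range sites used, nor who belongs to the FAS or PP set.

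**Conclusion.** Wrong as written: a text error in an eligibility threshold. About 4 to 6 of 184 infants would meet the printed range on one measurement if they resemble the reference population, and about 9 under the favourable assumption of perfect centring and half the spread, against at least 144 (78%) needed. The gap is too wide for any plausible distribution of unselected infants to close.

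Confidence that 25-27 is not the intended range is high, subject to the check of the digits. Confidence in any actual effect on enrolment is low, because only the summary is available. The consequence is conditional: infeasible recruitment if the rule is followed literally, or formal breaches of criterion 4 that discontinuation criterion 6 would cover if a wider range is used. It is worth correcting because sites must act on this line and the correction is cheap.

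**What to change.** 1. Check the digits against the PDF page and the full protocol.
2. Have the sponsor confirm and correct both centile bounds in criterion 4; the intended values should not be guessed.
3. State in the same line that the bounds apply to weight, length and head circumference.
4. Send the correction to sites.
5. Check that the 22% loss at screening and during the study is still consistent with the corrected range, and restate it if not.

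The cost is a text correction and a site notice, with a desk check of the loss figure. No new visits, measurements or analyses are needed. Whether the consent target changes depends on the confirmed range.

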6. Muscle relaxants (ATC group M03).
7. Antihypoxants and antioxidants (ethylmethylhydroxypyridine succinate, citicoline, etc.).
8. Agents improving metabolism and energy supply to tissues reducing tissue hypoxia (cytoflavin, corylip, eltacin, inosine, etc.).
9. Homeopathic products.
10. Vitamins and vitamin-like agents (ATC groups A11E, A11D, A11HA) – thiamine (vitamin B₁), pyridoxine (vitamin B₆), pyridoxal phosphate, nicotinic acid (vitamin PP), pantothenic (vitamin B₅) and pangamic (vitamin B₁₅) acids.
11. Products previously causing allergic reactions in the subjects.

Study design scheme

Schedule of study procedures

Procedure/visit	Visit 1 (Screening, Day 0)	Visit 2 (Week 4±5 days)	Visit 3 (Week 8±5 days)	Visit 4 (Week 12±5 days)
Signing patient information sheet	+			
Collection of complaints	+	+	+	+
Collection of medical history	+			
Objective examination	+	+	+	+
Neurological status	+	+	+	+
Body weight measurement	+			+
Body length measurement	+			+
Head circumference measurement	+			+
Evaluation of physical development by centile tables	+			+
Evaluation of psychomotor development using Jurba-Mastyukova scale	+	+	+	+
Evaluation of psychomotor development using CAT/CLAMS scale	+	+	+	+
Recording concomitant therapy	+	+	+	+
Evaluation of compliance with inclusion/exclusion criteria	+			
Randomization and prescription of the study therapy	+			
Drug issue	+	+	+	
Accounting and return of the product, determination of compliance		+	+	+
CGI score				+
Therapeutic safety evaluation		+	+	+

Statistical Analyses

The following rules and assumptions were taking into account when calculating the sample size: power of statistical criteria is equal to 80% (probability of non-missing the effect is equal to 0.8); probability of error of the first kind is $< 5\%$ (probability of erroneous decision on the effect presence < 0.05). The statistical criteria used are two-sided, sample size is based on the assumption of the expected effects according to the primary outcome measure claimed in the protocol.

It is supposed that the difference between proportions of subjects with increased Jurba-Mastyukova total score ≥ 4 scores by the end of the treatment course in Tenoten for children group compared to equivalent proportion of subjects in Placebo group is no less than 22% in favour of Tenoten for children.

Given the statistical terms mentioned above, the size of each group will be 72 subjects (PP analysis, total = 144).

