Supposing potential withdrawal of at least 22% subjects at screening and during the study for various reasons, at least 92 subjects in each group (184 in total) will be required to be recruited with their parents/adoptive parents signing informed consent form.

Safety and tolerability analysis of the study therapy will be based on the data from all randomized subjects who have received at least one dose of the study product/placebo. Efficacy analysis will be based on the two samples - FAS (Full Analysis Set) and PP (Per Protocol set): ITT-analysis and PP-analysis, respectively.

SAS-9.4 software will be used for statistical analysis including various parametric and nonparametric tests.

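### No baseline adjustment is pre-specified for the primary responder comparison, although entry Jurba-Mastyukova score and age are already collected and could sharpen it at almost no cost

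*Combined protocol and SAP*

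**What the plan says.** The primary endpoint is "Percentage of patients with a 4 and more point increase of the total score according to Jurba-Mastyukova psychomotor development scale", judged at the end of treatment against baseline. The Statistical Analyses section gives 80% power, a two-sided 5% error rate, 72 evaluable infants per group and a planning difference that "is no less than 22% in favour of Tenoten for children". It plans efficacy analyses on both the full analysis set and the per-protocol set. Its only statement of method is: "SAS-9.4 software will be used for statistical analysis including various parametric and nonparametric tests".

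On allocation, the Study design section says only that infants are "randomized at Visit 1 into one of the two groups". No stratification factor is given.

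Three other places bear on the point:

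- Inclusion criterion 3 sets the entry range: "Jurba-Mastyukova total score < 27 and > 12".
- Inclusion criterion 1 sets the age range: "Full-term infants aged 29 days to 9 months".
- The Schedule of study procedures has a row "Evaluation of psychomotor development using Jurba-Mastyukova scale" marked at Visit 1 and at every later visit. CAT/CLAMS is scored at the same visits.

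Secondary endpoint 2 is "Mean Cognitive adaptive test/Clinical linguistic and auditory milestone scale (CAT/CLAMS) by the end of the treatment course compared to baseline", with no statement of how the baseline value enters the analysis. The text is silent on adjustment; it does not rule it out.

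**The concern.** A fixed 4-point threshold on a change score does not adjust for where the infant started. An infant who enters at 13 responds on reaching 17, far below the protocol's own threshold of 27 for normal development. One who enters at 26 must reach 30, which is 3 points above that threshold. Age spans roughly eight months on a scale of infant development. Either variable could plausibly predict who gains 4 points, though the documents do not say how strongly.

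Two things are at stake:

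- **Precision.** If entry score and age predict response, leaving them out gives a wider interval and less power from the same 144 infants.
- **Pre-specification.** With test and covariates both left open, they can be chosen after the data are seen.

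**Working it through.** **Inputs from the documents.** Two-sided 5%, 80% power, a 22-point difference and 72 per group (Statistical Analyses).

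**Assumptions, because the documents give no figure.** Placebo responder rate p of 23%, 39% and 55%, with the active rate 22 points higher; covariate strength from none to strong.

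**Step 1: the plan's own figure.** The pooled two-proportion formula is

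n = [1.96·√(2p̄(1−p̄)) + 0.8416·√(p(1−p) + q(1−q))]² / 0.22², with q = p + 0.22 and p̄ = (p + q)/2.

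- p = 23% or 55%: (1.96·√0.4488 + 0.8416·√0.4246)² / 0.0484 = 71.6, so 72 per group. This matches the plan.
- p = 39%: (1.96·√0.5 + 0.8416·√0.4758)² / 0.0484 = 79.9, so 80 per group.

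The stated 72 is therefore attainable, but only for some placebo rates. Near 39 to 40% it falls short of 80% power.

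**Step 2: power with and without adjustment.** Monte Carlo with 72 per arm and 20,000 trials per cell. Response comes from a latent normal variable, with two standard-normal covariates sharing the stated R² equally and the marginal rates fixed at p and p + 22 points. Each cell gives the unadjusted chi-square power, then the adjusted logistic Wald power, in %. The Monte Carlo standard error is about 0.3 points.

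| Latent R² | p = 23% | p = 39% | p = 55% | Change in points |
|---|---|---|---|---|
| 0 | 80.6 / 80.4 | 77.4 / 75.7 | 79.9 / 79.9 | −1.6 to 0 |
| 5% | 79.8 / 81.1 | 77.1 / 76.8 | 80.5 / 81.4 | −0.3 to +1.2 |
| 10% | 79.9 / 82.4 | 77.2 / 77.9 | 80.3 / 82.2 | +0.7 to +2.5 |
| 20% | 80.4 / 84.7 | 77.2 / 80.7 | 80.3 / 85.0 | +3.6 to +4.7 |
| 30% | 80.1 / 87.6 | 76.5 / 83.4 | 79.8 / 86.9 | +6.9 to +7.5 |

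The changes were taken before rounding, so some differ by 0.1 from the rounded cells. Type I error was 4.8 to 5.1% adjusted and 4.9 to 5.6% unadjusted.

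**Step 3: width of the interval.** This is the mean 95% half-width, in points, for the standardised risk difference (model predictions averaged under each arm, influence-function standard error). The equivalent change in sample size is (unadjusted width / adjusted width)² − 1.

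| | p = 39% | p = 23% or 55% | Sample-size equivalent |
|---|---|---|---|
| Unadjusted | 15.82 | 14.94 | reference |
| R² 0 | 15.93 | 15.05 | about −1.5% |
| R² 10% | 15.43 | 14.60 | about +5% |
| R² 20% | 14.90 | 14.1 | about +12% |
| R² 30% | 14.36 | 13.63 | about +20% |

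Example: (15.82/14.90)² = 1.127. As a check on the reference row, 1.96·√(2 × 0.39 × 0.61/72) gives 15.9 points, in line with 15.82.

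**Step 4: the R² scale.** The R² above is latent. Latent 10% and 20% correspond to only about 5–6% and 11–13% of the variance of the yes/no response itself. On that second scale the effective sample size is 72/(1 − R²), so R² = 0.10 gives 72/0.90 = 80 per arm and R² = 0.20 gives 72/0.80 = 90. At p = 39% the normal-approximation power then goes from 75.7% to 80.1% and 84.5%.

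A separate simulation tested the standardised risk difference directly, again at p = 39%. Here R² is on the response scale:

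- R² = 0.095: variance ratio 0.905, power 76.6% to 79.5%.
- R² = 0.193: variance ratio 0.816, power 77.3% to 84.5%.
- R² = 0: variance ratio 1.005, power 77.9% to 76.9%.

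Once the scales are matched the two sets agree. For example, 1/(1 − 0.11) to 1/(1 − 0.13) is 1.12 to 1.15, close to the +12% in Step 3.

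**The case against.** The strongest reply is that this is an improvement rather than an error. An unadjusted comparison of randomised arms is valid, nothing in the document contradicts itself here, and the gain rests wholly on an assumed covariate strength. At a latent R² of 5% there is essentially no gain, and at a 39% placebo rate nothing clear appears until about 10%. Infants withdrawn because they need prohibited medicines count as failures. Baseline may not predict those failures, and the simulation does not model them. All of this stands, and it limits the claim to precision.

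A second reply is that the wider gap is the missing primary test, and that naming a plain two-proportion test would by itself prevent a choice after the data are seen. That is right for the pre-specification half of the concern. It does nothing for precision, and the fix below closes both gaps at once.

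Third, the fix tests a conditional effect but reports a marginal risk difference, so test and interval can disagree. In two simulations they did so in about 0.6–1.1% and 1.3–1.7% of trials, which is small.

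Fourth, the document calls itself a protocol summary, so a fuller plan may exist. None is in the documents supplied, so the absence is established only for this text.

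**Conclusion.** The concern holds. The document names no primary test, covariate or stratification factor, while two plausible prognostic variables are fixed before randomisation and need no new data.

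The size is uncertain because neither the placebo rate nor the prognostic strength is given. Over the assumed ranges the power change runs from a loss of about 1.6 points (no prognostic value) to a gain of about 7.5 (latent R² 30%). The 95% half-width, 14.9 to 15.8 points unadjusted, becomes 15.1 to 15.9 at R² 0 and 13.6 to 14.4 at R² 30%. At a 39% placebo rate, where 72 per arm gives about 77% power, adjustment restores roughly 80% if latent R² is 20%.

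The possible loss is small and the possible gain several times larger. The change should be made, but validity does not depend on it. Confidence is medium because the covariate strength is unknown.

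**What to change.** Before unblinding, add the following to the statistical section:

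- **Primary endpoint.** Logistic regression of response on treatment, with baseline Jurba-Mastyukova total score and age at randomisation as continuous covariates and a two-sided 5% test of the treatment term. Apply the same model to the full analysis set and the per-protocol set.
- **Reported effect.** The standardised (marginal) risk difference with its 95% confidence interval, so that the result can be read against the 22-point planning difference. The adjusted odds ratio is conditional on the covariates and is not a substitute. If the sponsor wants one procedure for both test and interval, the test can be based on this risk difference.
- **Mean CAT/CLAMS.** ANCOVA of the Week 12 value on treatment, baseline CAT/CLAMS and age.

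The cost is a few lines of text and minor programming, with no added visit, procedure or infant. If the covariates turn out not to be prognostic, the loss is at most about 1.6 points of power in the simulation.
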